#### **4.8.5. *Visit 5: 24 months follow up (±2 month)***

- VAS leg pain
- VAS back pain
- Questionnaires ODI, ZCQ, EQ-5D, patient satisfaction, status of employment / pension
- Physical examination
- Neurological status
- Pain management
- Hospitalization

- Follow up treatment
- X-ray images for both groups in all four positions
- CT Scan for all subjects
- Walking distance test

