**4.8.6. *Visit 6: 36 months follow up (±4 month)***

- VAS leg pain
- VAS back pain
- Questionnaires ODI, ZCQ, EQ-5D, patient satisfaction, status of employment / pension
- Physical examination
- Neurological status
- Pain management
- Hospitalization
- Follow up treatment
- X-ray images for both groups in all four positions
- Walking distance test

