**4.8.8. *Visit 8: 60 months follow up (±4 month)***

- VAS leg pain
- VAS back pain
- Questionnaires ODI, ZCQ, EQ-5D, patient satisfaction, status of employment / pension
- Physical examination
- Neurological status
- Pain management
- Hospitalization
- Follow up treatment
- X-ray images for both groups in all four positions
- CT Scan for symptomatic, confirmed spinous process fracture subjects
- Walking distance test

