#### **4.8.10. Schedule of Study Visits**

A tabular summary of visit schedule is provided below.

Visits	Screening		Follow-Up						Final Report
	1 < 4 weeks before d0	2 day 0 surgery	3 months after surgery (±2 weeks)	4 12 months after surgery (±2 month)	5 24 months after surgery (±2 month)	6 36 months after surgery (±4 months)	7 48 months after surgery (±4 months)	8 60 months after surgery (±4 months)	
Patient information and Informed consent	X								
Demographics	X								
Medical history	X								
Pain management	X	X 	X	X	X	X	X	X	
Physical examination	X 		X 	X 	X 	X 	X 	X 	
Neurological status	X	X 	X	X	X	X	X	X	
Inclusion/exclusion criteria	X	(X)							
X-ray in standing position (AP, lateral, flexion, extension)	X	X 	X	X	X 	X	X	X 	
MRI and/or Post Myelo CT (not older than 6 months)	X								
Diagnosis	X								
Walking Distance Test (treadmill)	X		X	X	X	X	X	X	
VAS back pain, VAS leg pain	X		X	X	X			X	
ODI, ZCQ, EQ-5D	X		X	X	X	X	X	X	
Surgery		X							
Patient's satisfaction questionnaire			X	X	X	X	X	X	
Documentation of AEs		X	X	X	X	X	X	X	

1) A detailed physical examination will be performed at visit 1. In the following visits only a routine physical examination will be performed and changes compared to screening will be recorded. The investigator is free to perform a complete physical examination.

2) Only group B (with coflex® implant: anterior-posterior, lateral).

3) After surgery, before discharge.

4) CT Scans will be conducted at 24 months for all subjects and at 60 months for all symptomatic, confirmed spinous process fracture subjects.

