#### **4.13. Subject Discontinuation**

Patients which did not receive a patient number will be replaced – they will be judged as screening failures. At the end of the initial recruitment phase of 406 patients that fulfil all in-/exclusion criteria should be allocated to the study.

In order to meet 406 treated study patients those patients that are excluded by the investigator during the surgery will be replaced.

The patient is entitled to terminate the clinical investigation at any time without giving any reason and without having to expect any disadvantages by the Investigator.

Reasons for withdrawal of a patient from the clinical investigation may be:

- Insufficient cooperation of the patient (non-compliance with study procedures);
- Technical or administrative reasons (change of Investigator, move of the patient);
- Withdrawal of Informed Consent;
- Death

Pregnancy will not be a reason for discontinuation. The number of x-rays taken will be limited.

For patients who terminate the clinical investigation prematurely, a complete final examination has to be performed if the patient is still available for an examination.

For this final examination all assessments as planned for Visit 5 have to be carried out.

If the patient cannot come to a final examination the Investigator should clarify the reason and time point for discontinuation/drop out by phone and document this in the source document used at the site. In case of drop outs due to an (S)AE the Adverse Event has to be documented sufficiently in the SAE form and the Investigator has to report the SAE to the sponsor within 24 hours (see section about SAE reporting).

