#### **5.2.7. Spinous Process Fracture**

Spinous process fractures will be assessed from X-ray at all time points and CT at 24 months. Subjects with confirmed, symptomatic spinous process fractures will also have CT taken at 60 months. All X-rays and CTs from all centers will be evaluated centrally by an experienced, independent radiologist. Presence of spinous process fractures will not be considered a treatment failure.

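### The early-termination examination in 4.13 repeats the all-subject CT for patients who leave after their Month 24 CT, a second scan that the schedule reserves for symptomatic, confirmed spinous process fracture

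*Combined protocol and SAP*

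**What the plan says.** For patients who end the study prematurely, section 4.13 states that "a complete final examination has to be performed if the patient is still available for an examination". It then fixes the content: "For this final examination all assessments as planned for Visit 5 have to be carried out". If the patient cannot come, the investigator clarifies the reason and time of dropout by phone.

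The Visit 5 list (4.8.5, Month 24) contains "CT Scan for all subjects". No other visit has a CT for everyone:

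- Visit 6 (4.8.6) lists "X-ray images for both groups in all four positions" and no CT. Visit 7 (4.8.7) has the same imaging.
- Visit 8 (4.8.8) lists "CT Scan for symptomatic, confirmed spinous process fracture subjects".
- Footnote 4 of the schedule (4.8.10) summarises: "CT Scans will be conducted at 24 months for all subjects and at 60 months for all symptomatic, confirmed spinous process fracture subjects".
- Section 5.2.7 adds: "Spinous process fractures will be assessed from X-ray at all time points and CT at 24 months". It repeats the Month 60 restriction and has all X-rays and CTs read centrally.
- Section 4.7.7 names only Month 24 and Month 60 CT images for collection and leaves confirmation of fractures to the core lab.

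4.13 contains one limit on imaging: "Pregnancy will not be a reason for discontinuation. The number of x-rays taken will be limited". It says nothing about repeating a CT.

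**The concern.** The sponsor chose to restrict any CT after Month 24 to patients with a symptomatic, confirmed fracture. Copying the whole Visit 5 list into the exit examination lifts that restriction for one group: patients without such a fracture who have had the Month 24 CT, leave before Month 60 and attend the final examination. For example, a patient who leaves at Month 30 is scanned again about six months after the first CT.

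Two things are at stake. The first is radiation: a patient who is leaving receives a CT that the same patient would not have had by staying. The second is comparability: patients without such a fracture who remain in the study have no CT after Month 24, so the exit scan has nothing to be compared with. Neither touches the primary composite endpoints.

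**Working it through.** The plan states no figure for CTs per patient, so there is nothing to reproduce. The check is a cross-reading of sections followed by a count.

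**Step 1. What the exit examination contains.** 4.13 calls for every Visit 5 assessment, in mandatory terms, for any early leaver who is available. 4.8.5 puts one CT in that list for all subjects. The exit examination therefore adds 1 CT, whatever the time of leaving and whatever scans came before.

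**Step 2. What the schedule plans.** From 4.8.5 to 4.8.8, footnote 4 and 5.2.7: 1 CT at Month 24 for everyone, 0 at Visits 6 and 7, and 1 at Month 60 only with a symptomatic, confirmed fracture. Follow-up is 60 months per patient (Synopsis), so there is time to leave after the Month 24 CT.

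**Step 3. Study CTs per patient.** Total = Month 24 CT + Month 60 CT + exit CT.

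| Patient | Current 4.13 | With the fix |
|---|---|---|
| No such fracture, completes Month 60 | 1 + 0 + 0 = 1 | 1 |
| No such fracture, leaves before the Month 24 CT, attends | 0 + 0 + 1 = 1 | 1 |
| No such fracture, leaves before the Month 24 CT, does not attend | 0 | 0 |
| **No such fracture, leaves after the Month 24 CT, attends** | **1 + 0 + 1 = 2** | **1** |
| No such fracture, leaves after the Month 24 CT, does not attend | 1 | 1 |
| Symptomatic, confirmed fracture, completes Month 60 | 1 + 1 + 0 = 2 | 2 |
| Symptomatic, confirmed fracture, leaves after the Month 24 CT, attends | 1 + 0 + 1 = 2 | 2 |

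Only the row in bold exceeds what the schedule plans for that kind of patient, by 2 − 1 = 1 scan. A patient who leaves before the Month 24 CT has a single CT earlier than planned, not an additional one.

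**Step 4. Whether planned data depend on the extra scan.** Spinous process fracture is a secondary radiographic endpoint (3.3). 5.2.7 assesses it by X-ray at all time points and by CT at Month 24, with the restricted CT at Month 60. X-rays in all four positions are also in the Visit 5 list, so they remain in the exit examination. An exit CT would be read centrally and could show a fracture, but no endpoint names a CT time point other than Months 24 and 60. 5.2.7 also says that a spinous process fracture is not a treatment failure, so no composite success endpoint depends on the scan.

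**The case against.** The best defence is that an exit examination modelled on the fullest follow-up visit is a recognisable choice. Ordering a CT for everyone at Month 24 on top of X-rays suggests that X-ray alone is not regarded as fully sufficient, and a last CT before follow-up ends could be deliberate. It would not be useless: 5.2.7 has all CTs read centrally, and 3.3 sets no modality or time limit for fracture. A reader might infer that the scan serves no planned endpoint, and that goes too far. It could contribute to the fracture assessment, but at a time no endpoint names and without a counterpart in comparable patients who stay.

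A reader might also infer that 4.13 contradicts the schedule. It does not, because no sentence forbids a CT at withdrawal. The scan is an addition that the schedule does not plan.

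A site could read the reference to what is planned for Visit 5 narrowly, since footnote 4 ties the all-subject CT to Month 24, and treat it as done. That reading is possible but weaker, because the text asks for all assessments and offers no option to omit one.

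A number of affected patients might be inferred from the 15% allowance in 4.2. The documents do not support this. The allowance is a planning figure for loss to follow-up, 7.11.1 names withdrawals separately, and patients lost to follow-up are the least likely to attend an exit visit. No attendance rate or exit timing is given, and death and withdrawn consent are among the listed reasons for leaving.

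One practical objection stands and shapes the fix. Because the core lab confirms fractures, one first seen on the exit X-ray is not yet confirmed at that visit. An exception limited to confirmed fractures would miss that patient or require recall.

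**Conclusion.** The point holds, as a minor one. Followed as written, 4.13 gives 1 extra study CT (2 instead of 1) to each patient without a symptomatic, confirmed spinous process fracture who leaves after the Month 24 CT and attends the final examination. Other patients' counts already match the schedule or fall below it. The documents give neither the number of such patients nor a radiation dose, so the total burden cannot be stated. Sample size, power, type 1 error and the primary analyses are unaffected.

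The conclusion assumes that sites follow the wording of 4.13 literally. It rests on the main protocol text. The Radiographic Protocol (Appendix V) and the example consent text (Appendix III) are listed but were not available, and either could contain a rule on repeat imaging. 4.13 does not refer to them.

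**What to change.** Keep the Visit 5 list in 4.13 and add to the sentence: *except that the CT is not repeated once the Month 24 CT has been done, unless the patient has a symptomatic spinous process fracture that is confirmed or is suspected on the exit X-ray*.

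This keeps the CT for patients who leave before having it, and for those with a symptomatic fracture not yet confirmed by the core lab. It is safer than switching to the Visit 8 list. That would drop the CT for most patients who leave before Month 24, and could put in doubt the record of pain-killer type, which 4.7.8 captures only at Visits 1 to 5.

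The cost is one clause and a small loss of information: an asymptomatic late fracture visible only on CT would not be recorded at exit. The same is already true of patients who complete Month 60. No analysis needs to change.

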#### **4.14. Trial Materials**

##### **4.14.1. Description of the Study Device**

As the coflex implant is approved for market, the devices used for the study originate from the normal production and have to be handled according to the product brochure and manufacturers information.

##### **4.14.2. Labeling**

As the study device (coflex Implant) is already PMA approved, the devices used for this trial will not be labelled separately for this trial, i.e. no text like "for clinical investigation only" will be mentioned. Devices from the normal production will be used and the legal requirements for labelling PMA-approved (US) will be fulfilled.

#### **4.14.3. Device Accountability**

There will be no device shipments because of the trial. The devices routinely available at each center will be used for the study patients.

A device accountability form will therefore not be filled in. Any coflex device used with a patient will be documented (lot no. and size) in the eCRF.

### **4.15. Trial Documents:**

The following documents have to be available before shipment of trial supplies to the trial center:

- A signed protocol and amendment(s), if any;
- A copy of the dated and signed written approval from the IRB of the protocol, amendment(s) (if any), Informed Consent Form, and any applicable recruiting materials. This approval must clearly identify the trial by title and number;
- A statement if the IRB is compliant with ICH-GCP guidelines, the names of the current members or composition of the IRB and their position in the health-care institution or their credentials, and the working procedures of the committee.
- Regulatory authority approval
- Signed Investigator's agreement (modified FDA Form 1572), if applicable,
- FDA Financial Disclosure Questionnaire, if applicable,
- A copy of the Signature Authorization Log that enlists all people involved in the trial at a center;
- The curricula vitae of the Investigator, co-Investigators and other study material (if any);
- The signed Financial Agreement.

#### **4.15.1. Electronic Case Report Forms (eCRFs)**

Electronic Case Report Forms (eCRFs) are to be completed for all subjects.

All data is entered into the Electronic Clinical Data Management System by the Study Coordinator or by the patient directly (patient questionnaires).

The Investigator must verify that all data entries in the eCRFs are accurate and correct. If certain information is "Not Done", "Not Available" or "Not Applicable", the Investigator must enter "n.d." or "n.av." or "n/a", respectively, in the appropriate space.

All data will be reviewed for consistency and correctness with the protocol by the Data Management team at the CRO. All discrepancies requiring verification via an examination of the source documents will be sent to the study site for resolution or resolved during Monitoring visits. During monitoring visits, the Clinical Research Associate (CRA) will also review all data, evaluate for completeness and have the study coordinator enter missing information and/or resolve errors with the Investigator. All entries, corrections and alterations are to be made by the responsible Investigator or his/her designee.

An electronic audit trail will be maintained to track all changes to the database.

#### **4.15.2. Documentation Files**

The Sponsor's Investigator file will include all relevant documents that are filed in the Investigator file and additional internal information (e.g., internal communication Sponsor-CRO). The CRO file will contain all study related documents including all internal and external communication.

All data about X-rays will be kept for at least 30 years after completion of the study.

#### **4.15.3. Essential Documents for the Conduct of a Clinical Trial**

The Investigator file will be provided to the Investigator at the Study Initiation Visit. It is required by law that the Investigator keeps this file updated and in good condition during the entire study.

The Investigator file contains the essential documents for the conduct of a clinical trial:

- Instructions for Use
- Protocol and Amendment(s)
- Protocol and Amendment(s) Signature Page(s)
- Financial Disclosure(s) for Investigator and Sub-Investigator(s)
- Core Laboratories Certifications and Procedures
- Investigator Agreement or FDA Form 1572
- Delegation of Authority Log
- Curriculum Vitae (Investigator, Sub-Investigator(s), Study Staff)
- Medical License (Investigator, Sub-Investigator(s), Study Staff)
- Subject Protection/GCP Training (Investigator, Sub-Investigator(s), Study Staff)
- IRB Submissions/Approvals:
  - Original Study/Protocol
  - Protocol Amendments
  - Informed Consent (all version)
  - Advertisements
  - Other Written Subject Information
- Interim or Annual Reports to IRB/EC
- Site Specific SAE/UADE Reports to IRB/EC
- Site Specific Deviation Reports to IRB/EC
- IRB Membership List, Assurance Number or Statement of Compliance
- Subject Screening and Enrollment Log
- Monitoring Visit Sign-In Log
- Clinical Trial Agreement
- Monitoring Visit Confirmation and Follow-Up Communications
- Study Communications

#### **4.16. Archiving:**

The Investigator shall maintain the Investigator file, which contains the trial documents as specified in “Essential Documents for the Conduct of a Clinical Trial” mentioned above and as required by the applicable regulatory requirement(s).

The Investigator should take measures to prevent accidental or premature destruction of these documents.

Essential documents shall be retained for 2 years in the study site and with the Sponsor after completion of the study. Under no circumstances shall the Investigator relocate or dispose any trial documents before having obtained written approval of Paradigm Spine. This also applies if the archiving period of 2 years has come to an end.

Any difficulty in storing original documents must be discussed with the Clinical Research Associate as soon as possible.

## 5. Performance Evaluation and Measurements

### 5.1. Primary Variables of Performance

Month 60 composite success will require the following items (Objective 1):

- At least a 15 point improvement relative to pretreatment baseline in the Oswestry Disability Index (ODI, range 0-100).
- No reoperations, revisions, removals, or supplemental fixation at the index level(s);
- No  $\geq 2$  injections or series of injections for any lumbar level\*\*, or nerve block procedures performed to treat spinal stenosis at any lumbar level(s); or a single injection within 12 months of the 5 year endpoint.

\*\*A series of injections is considered 2-3 injections performed between 24-hour and one week intervals designed to treat a single pain event. Secondary injections performed due to patient demand or recurrence of symptoms following the initial injection are considered separate injections and would constitute a study failure.

For Objectives 2 and 3, the Month 24 CCS from the IDE will be slightly modified to include any surgical intervention at index level(s). This is because the decompression only group receives no device. In summary, when comparing coflex® in conjunction with decompression to decompression alone, Month 24 CCS will require.

- No “Treatment Failure” on or before the exact 2-year anniversary of the index surgery).
- At least a 15 point improvement relative to pretreatment baseline in the Oswestry Disability Index (ODI, range 0-100).
- No persistent new or worsening sensory or motor deficit where persistence is established by identifying new or worsening deficits at Month 12 that do not resolve by Month 24.
- No major device-related adverse event defined as an event simultaneously both ‘Serious’ and ‘Definitely’ related to the implant on or before the exact surgical two-year anniversary.

Treatment Failure will include:

- No surgical intervention at the index level
- No lumbar epidural steroid injection including nerve root blocks and facet blocks at any lumbar level.

The identical Month 24 CCS endpoint used in the IDE study will be used to compare PAS results to IDE study results and to update the Bayesian posterior probabilities of non-inferiority and superiority relative to fusion (Objective 4).

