	the PAS population relative to device performance defined by IDE study results.
CRITERIA for EVALUATION: 1. EFFECTIVENESS	
Objective 1: Month 60 Composite Clinical Success (CCS)
 
A similar CCS endpoint as was used in the IDE will be used to compare clinical status of patients implanted with the coflex® device relative to surgical decompression at 60 months.
 
Month 60 success for this comparison will require the following items:
 
 
❖ At least a 15 point improvement relative to pretreatment baseline in the Oswestry Disability Index (ODI, range 0-100).
 
❖ No reoperations, revisions, removals, or supplemental fixation at the index level(s);
 
❖ No <math>\geq 2</math> injections or series of injections for any lumbar level**, or nerve block procedures performed to treat spinal stenosis at any lumbar level(s); or a single injection within 12 months of the 5 year endpoint.
 
 
**A series of injections is considered 2-3 injections performed between 24-hour and one week intervals designed to treat a single pain event. Secondary injections performed due to patient demand or recurrence of symptoms following the initial injection are considered separate injections and would constitute a study failure.
 
Additional details, justification, and sensitivity analyses are described in the main protocol text below.
 
Objectives 2 and 3: Month 24 CCS
 
For the comparison to decompression, the Month 24 CCS will be slightly modified to include any surgical intervention at index level(s). This is because the decompression only group receives no device. In summary, when comparing coflex® in conjunction with decompression to decompression alone, Month 24 CCS will require:
 
 
• No “Treatment Failure” on or before the exact 2-year anniversary of the index surgery. Treatment Failure will include: 
 
1. No surgical intervention at the index level
 
2. No lumbar epidural steroid injection including nerve root blocks and facet blocks at any lumbar level
 
 
 
• At least a 15-point improvement relative to pretreatment baseline in the Oswestry Disability Index (ODI, range 0-100).
 
• No major device-related adverse event defined as an event simultaneously both 'Serious' and 'Definitely' on or
 

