## 2. Rationale

The coflex® Interlaminar Technology has been in clinical use for more than 10 years and is CE-certified according to the standards. Prior to US approval, only isolated, retrospective data for the clinical success is available (Samani 2000^5, Kaech et al. 2002)

In a clinical study to support US market approval, three hundred twenty-two randomized patients (215 coflex® and 107 fusions) from 21 sites in the United States were enrolled between 2006-2008. Subjects received laminectomy and coflex® interlaminar stabilization or laminectomy and posterolateral spinal fusion with spinal instrumentation in a 2:1 ratio. Overall device success required a 15-point reduction in ODI, no reoperations, no major device-related adverse events, and no post-operative epidural injections.

In this study, coflex® patients experienced significantly ( $p<0.0001$ ) shorter operative times (mean 98 min vs 153 min), less blood loss (mean 110 cc vs 349 cc), and length of stay (mean 1.9 vs 3.2 days). Among patients with no Treatment Failure (no reop and no lumbar injection), there was a trend towards significantly better improvement in mean ODI scores in the coflex® cohort compared to fusion (Month 24 mean 22.0 vs 26.7,  $p=0.075$ ). Both groups demonstrated significant improvement from baseline in all VAS Back and Leg parameters. Among non-Treatment Failures, coflex® patients experienced greater SF-12 Physical Health outcomes ( $p=0.050$ ) and equivalent Mental Health outcomes. coflex® subjects experienced better Month 24 ZCQ outcomes compared with fusion (Symptom Severity ( $p=0.023$ ); Physical Function ( $p=0.008$ ); Satisfaction ( $p=0.006$ )).

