##### **Objective 2:**

The second objective of this study is to compare clinical status of patients implanted with the coflex® device in conjunction with surgical decompression relative to surgical decompression alone at two years post operatively by confirming clinical non-inferiority in terms of Month 24 composite clinical success (CCS) defined similarly to the IDE study endpoint. This objective will be achieved by conducting a Bayesian test of the null hypothesis that the probability of achieving

Month 24 CCS among patients implanted with the coflex® device in conjunction with surgical decompression is no more than 10% smaller than that for patients undergoing surgical decompression alone. An informative prior distribution for the coflex® group was formulated on the basis of results contained in the coflex® SSED.

For the comparison to decompression, the Month 24 CCS will be slightly modified to include any surgical intervention at index level(s). This is because the decompression only group receives no device. In summary, when comparing coflex® in conjunction with decompression to decompression alone, Month 24 CCS will require:

- No “Treatment Failure” on or before the exact 2-year anniversary of the index surgery. Treatment Failure will include:
  1. No surgical intervention at the index level
  2. No lumbar epidural steroid injection including nerve root blocks and facet blocks at any lumbar level
- At least a 15 point improvement relative to pretreatment baseline in the Oswestry Disability Index (ODI, range 0-100).
- No major device-related adverse event defined as an event simultaneously both ‘Serious’ and ‘Definitely’ on or before the exact surgical two-year anniversary or exact five-year anniversary. In the decompression alone group, since there is no device, this endpoint will be identified as any serious AE that is classified as definitely related to surgery.

**Note:** The IDE study defined this CCS component as severe and definitely-related and not as serious and definitely-related. This has been changed to serious and definitely related for consistency with other spine studies for Objectives 2 and 3 only.

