### **3.2. Primary Endpoints**

The identical Month 24 CCS endpoint as was used in the IDE will be used to compare PAS results to IDE study results, and to update the Bayesian posterior probabilities of non-inferiority and superiority relative to fusion. This CCS definition requires no Treatment Failure (i.e., no reoperation, revision, replacement, or supplemental fixation at the index level(s) and no epidural injection at any lumbar level); an ODI improvement  $\geq 15$ ; as well as no new or worsening, persistent neurological deficit; and no major device-related adverse event defined as severe and definitely-related

The CCS endpoints using in Objective 2 and 3 replace severe device-related AEs with serious device-related AEs for greater consistency with other spine studies. The relationship will be evaluated relative to the device and the surgical procedure since controls receive no device. For comparison to decompression alone, any surgical intervention at the index site will imply clinical failure.

Month 60 success for this comparison will require the following items:

- At least a 15 point improvement relative to pretreatment baseline in the Oswestry Disability Index (ODI, range 0-100).
- No reoperations, revisions, removals, or supplemental fixation at the index level(s);
- No  $\geq 2$  injections or series of injections for any lumbar level\*\*, or nerve block procedures performed to treat spinal stenosis at any lumbar level(s); or a single injection within 12 months of the 5 year endpoint.

\*\*A series of injections is considered 2-3 injections performed between 24-hour and one week intervals designed to treat a single pain event. Secondary injections performed due to patient demand or recurrence of symptoms following the initial injection are considered separate injections and would constitute a study failure.

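### The Month 24 composite for Objectives 2 and 3 has three requirements in the synopsis and section 3.1 but four in section 5.1, which adds a persistent neurological deficit, and no text says which list governs.

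*Combined protocol and SAP*

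**What the plan says.** The synopsis introduces the Objectives 2 and 3 endpoint with "when comparing coflex® in conjunction with decompression to decompression alone, Month 24 CCS will require" and lists three requirements: no treatment failure by the two-year anniversary (index-level surgery or lumbar injection), an ODI gain of at least 15 points, and no serious, definitely related event. Section 3.1, Objective 2, uses the same lead-in and the same three. Neither list has a neurological requirement.

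Section 5.1 introduces the same endpoint in nearly the same words and lists four. The addition is "No persistent new or worsening sensory or motor deficit where persistence is established by identifying new or worsening deficits at Month 12" that has not resolved by Month 24.

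Three other places bear on the question:

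- Section 3.2 describes the IDE composite as including "as well as no new or worsening, persistent neurological deficit". For Objectives 2 and 3 it names two changes: the adverse event item and the surgery item.
- The Note in section 3.1 declares only the move from severe to serious: "This has been changed to serious and definitely related for consistency with other spine studies for Objectives 2 and 3 only".
- Section 5.2.5 says that a neurological summary variable is part of the composite, but it measures persistence from Month 18.

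**The concern.** This endpoint decides the two-year non-inferiority test (Objective 2) and the superiority test that follows it (Objective 3). Sections 7.4 and 7.5 state hypotheses on Month 24 CCS without saying which list applies. A programmer working from the synopsis and one working from section 5.1 would class some patients differently.

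The prior is also affected. The coflex prior, beta(135.5, 69.5), comes from 135 of 204 successes on the IDE composite (section 7.7.2). If that composite contains the neurological item, as section 3.2 says, a three-item study endpoint is easier to meet than the endpoint behind its prior, and nothing in the plan declares that difference.

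**Working it through.** **Lists side by side**

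| Place | Neurological item in Month 24 CCS, Objectives 2 and 3 | Persistence measured from |
|---|---|---|
| Synopsis, effectiveness criteria | absent | not applicable |
| 3.1, Objective 2 | absent | not applicable |
| 3.2 | kept by implication | not stated |
| 5.1 | listed | Month 12 |
| 5.2.5 | said to be in the composite | Month 18 |

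The synopsis does mention a persistent deficit elsewhere, but only in the secondary, narcotics-modified composite, and there from Month 18. Sections 3.3 and 5.2 give that same secondary composite with Month 12. The schedule in 4.8.10 has follow-up at Months 3, 12, 24, 36, 48 and 60, so there is no Month 18 examination.

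Section 5.2.5 supports the item but does not settle the matter. It also speaks of a neurological item for Month 60 CCS, and the Month 60 lists in 3.1, 3.2 and 5.1 contain none.

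**Test case.** Take a patient with ODI improved by 15 points, no index-level surgery, no lumbar injection, no serious and definitely related event, and a new motor deficit at Month 12 still present at Month 24. Under the synopsis and 3.1 this is a success. Under 5.1 it is a failure. If the deficit is itself a serious, definitely related event, the patient fails under either list. Only neurological-only failures change status.

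**Effect on the treatment difference.** Let f be the share of an arm's patients who fail on the neurological item alone. Then four-item rate = three-item rate − f, and

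four-item difference = three-item difference − (f_coflex − f_control).

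Equal shares leave the difference unchanged. If the deficit instead strikes an equal proportion of otherwise successful patients, say 6% (assumed) at the planning rates 0.662 and 0.642, the arms lose 0.662 × 6% = 3.97 and 0.642 × 6% = 3.85 points, and the difference moves by 0.12 points. The documents give no value for f in either arm. For an assumed 1% to 5%, 150 × f = 1.5 to 7.5 patients per arm would change status.

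**Prior mismatch, for scale only.** The Objective 2 rule was evaluated exactly, over all outcomes, with 150 per arm, coflex prior beta(135.5, 69.5), control prior beta(0.5, 0.5), margin −0.10 and threshold 0.95. At true rates 0.662 and 0.642 this gives 86.4% power, against 89% in section 7.7.2. The simulation memo is not in the documents, so the gap is not called an error, and 86.4% serves only as the baseline here.

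Treat 0.662 as the four-item rate, drop the item, raise both true rates by the same f, and leave the prior at 66.2%:

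| Assumed f | True rates for power | Power | Type 1 error (control 0.10 higher than coflex) |
|---|---|---|---|
| 0% | 0.662, 0.642 | 86.4% | 0.033 |
| 1% | 0.672, 0.652 | 83.6% | 0.023 |
| 2% | 0.682, 0.662 | 80.3% | 0.015 |
| 5% | 0.712, 0.692 | 68.3% | 0.004 |

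The true difference is the same in every row. The loss of power comes only from a prior that sits below the easier endpoint, and under this assumption it works against coflex.

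**The case against.** The best defence is that the text already leans one way. Section 3.2 starts from an IDE composite with the item and names only two changes. The Note in 3.1 declares only one. Section 5.1 lists the item and section 5.2.5 says it belongs. No section says it was removed. The likeliest explanation is an omission from two lists. This stands, and it answers a stronger inference that a reader might draw, namely that the definition is open and could be picked freely once the data are in. What remains is that the synopsis and 3.1 are itemised lists of requirements, and no rule of precedence says that 5.1 overrides them.

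A reader might also infer that the Objective 4 endpoint is unclear, because section 2 sums up IDE success as "Overall device success required a 15-point reduction in ODI, no reoperations, no major device-related adverse events, and no post-operative epidural injections", with no neurological item. The documents do not support that. Section 2 is a one-sentence background summary of a past trial. The endpoint for Objective 4 is spelled out in section 3.2, with the item.

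A third inference is that the conflict moves the treatment difference by some stated part of the 10-point margin. That would need a gap between the arms in neurological-only failures, and the documents give none.

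**Conclusion.** The point holds as an internal inconsistency in a confirmatory endpoint, not as a criticism of a design choice. The synopsis and 3.1 conflict with 5.1, and 3.2 and 5.2.5 side with 5.1. Patients whose only failure is a persistent neurological deficit are classed by whichever section is followed.

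The number of such patients is unknown, and so is any effect on the treatment difference, which nearly cancels if the rate is equal in both arms. The power figures rest on assumed rates and show only that the item should match between the endpoint and its prior. That the IDE endpoint contained the item rests on section 3.2 alone. Even with four items, the two declared changes (serious for severe, and any index-level surgery) still separate the study endpoint from the one behind the prior, but those are stated openly.

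**What to change.** Before outcomes are unblinded, state one four-item list for Objectives 2 and 3, word for word the same, in the synopsis, 3.1, 3.2 and 5.1: no treatment failure, ODI improvement, no persistent new or worsening sensory or motor deficit, and no major related event.

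In the same edit, replace Month 18 with Month 12 to Month 24, as in 5.1, in section 5.2.5 and in the synopsis entry for the narcotics-modified composite. Otherwise the new list would still conflict with 5.2.5 and refer to a visit that does not exist.

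Reporting the three-item version as a sensitivity analysis is optional.

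The cost is wording only. Neurological status is already examined at Months 12 and 24 in both arms, and neither the sample size nor the prior has to change.
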